#### **9.3.1 Efficacy (Part 2)**

##### **9.3.1.1 Primary Efficacy Endpoint(s)**

The primary response measure is IOP. Two consecutive measurements of IOP will be taken for each eye, with the right eye measured first. If the first two measurements of either eye differ by more than two mm Hg, a third measurement will be taken for the eye. Depending on the number of measurements required and obtained, the IOP for a given eye will be represented by either the average or the median of the readings. Details will be provided in the SAP.

The change from baseline for each eye at each post-baseline assessment is calculated as the IOP at that assessment minus the IOP at the corresponding hour at baseline. Efficacy will be evaluated in the study eye. The study eye is the eye that meets the inclusion/exclusion criteria. If both eyes meet the criteria, the study eye will be the eye with the worse (highest) IOP at Day -1 Hour 0. If both eyes have the same IOP value at this timepoint, the right eye will be the study eye.

The primary efficacy endpoints are the Day 14/Exit mean IOP changes from Baseline (Day -1) at each time-matched hour (0, 2, 4, 8). The primary hypothesis is that AGN-227535 ophthalmic solution effectively lowers IOP. The primary efficacy analysis is the within-

group mean change from baseline at Hour 2, the time of peak efficacy of timolol. This study will also assess if AGN-227535 is non-inferior to Timolol ophthalmic solution 0.5% with respect to change from baseline (follow-up minus baseline) in study eye IOP at each time-matched hour evaluated (hours 0, 2 4, and 8) at Day 14/Exit in the mITT population. The analyses will be performed via analysis of covariance (ANCOVA) which will have treatment as the main effect and the Baseline hour-matched IOP as the covariate in the model.

Pairwise treatment group comparisons will be performed for each individual dose of AGN-227535 versus timolol ophthalmic solution 0.5%. A 2-sided 95% confidence interval (CI) for the treatment difference (AGN-227535 Ophthalmic Solution minus Timolol ophthalmic solution 0.5%) will be constructed based on this ANOVA model for each AGN-227535 dose.

If AGN-227535 ophthalmic solution is determined to be non-inferior to Timolol ophthalmic solution 0.5%, a further attempt to show superiority of AGN-227535 over Timolol will be made.

Primary efficacy will be evaluated in the mITT population.

### **9.3.1.2. Secondary Efficacy Endpoint(s)**

Mean IOP at Day 14/Exit.

Mean IOP change from baseline at each time-matched hour via analysis of variance (ANOVA) which will have treatment and the Baseline IOP stratum (IOP  $\leq$ 25 mm Hg and  $>$  25 mm Hg as the main effects in the model.

### **9.3.2. Safety Analyses**

All safety analyses will be performed on the Safety Population.

The Medical Dictionary for Regulatory Activities (MedDRA) nomenclature will be used to code adverse events. A detailed definition of treatment emergent adverse events (TEAEs) will be provided in the SAP. The number and percent of subjects with adverse event reports will be tabulated for all treatment emergent adverse events (TEAEs) regardless of causality, treatment-related TEAEs, all serious TEAEs, treatment-related serious TEAEs, and all adverse events leading to premature discontinuation of study treatment.

For Part 2, analyses of macroscopic hyperemia and hyperemia as evaluated on biomicroscopy will include evaluation of peak severity at each post-baseline visit (Days 4 and 14) and across all post-baseline time points.

Detailed methods for analyses of all safety variables will be provided in the SAP.

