### **9.3. Methods of Analyses**

In general, data will be summarized with descriptive statistics which will include sample size, mean, standard deviation, median, minimum and maximum for continuous variables and frequency and percentage for categorical variables.

Part 1: All safety and IOP-lowering effects tabulations will provide descriptive statistics by cohort.

Part 2: For continuous variables, treatment groups will be compared using analysis of variance covariance techniques or two-sample t-tests. Nominal variables will be analyzed using Pearson's chi-square test or Fisher's exact test.

Analyses performed for the mITT population will use the method of last observation carried forward (LOCF) to impute missing values. No imputation for missing data will be performed for the PP or safety populations.

As this is an exploratory trial, all treatment comparisons will be made at the two-sided  $\alpha = 0.05$  level without adjustment for multiple comparisons.

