#### **12.2.1.7. Clinical Safety Laboratory Assessments (non-fasting)**

The investigator must review the laboratory report, document this review, and record any clinically relevant changes occurring during the study in the AE section of the eCRF.

Clinically significant abnormal laboratory findings are those which are not associated with the underlying disease, unless judged by the investigator to be more severe than expected for the participant's condition. The laboratory reports must be filed with the source documents.

All laboratory tests with values considered clinically significantly abnormal during participation in the study or within [insert timeframe] after the last dose of study treatment should be repeated until the values return to normal or baseline or are no longer considered clinically significant by the investigator or medical monitor.

- If such values do not return to normal/baseline within a period of time judged reasonable by the investigator, the etiology should be identified and the sponsor notified;
- All protocol-required laboratory assessments (see below) must be conducted in accordance with the Laboratory Manual and the Schedule of Visits and Procedures;

Laboratory assessments will include blood chemistry panel, hematology including complete blood count with differential, urinalysis and urine pregnancy test for all females who are of child-bearing potential (See Section 6.4 for definition).

The specific tests in these panels are:

**Complete Blood Count** (with differential): hematocrit, hemoglobin, red and white cell count, mean corpuscular volume (MCV), mean corpuscular hemoglobin (MCH), mean corpuscular hemoglobin concentration (MCHC), red blood cell morphology, reticulocyte count, platelet count, neutrophils (bands and segments), lymphocytes, monocytes, eosinophils, and basophils.

**Chemistry Panel:** albumin/globulin (A/G ratio), alanine aminotransferase (ALT), aspartate aminotransferase (AST), gamma-glutamyl transpeptidase (GGT), albumin, alkaline phosphatase, bilirubin (total, direct, and indirect), blood urea nitrogen (BUN), BUN/creatinine ratio, calcium, magnesium, cholesterol, high-density lipoprotein (HDL), low-density lipoprotein (LDL), chloride, creatinine, globulin, hemoglobin A1c (HbA1c), lactic dehydrogenase (LDH), phosphorus, potassium, serum bicarbonate, total protein, sodium, triglycerides, uric acid, and creatine phosphokinase (CPK).

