### 5.4 Safety Endpoints

All safety analyses will be performed on the Safety Population.

Safety and tolerability will be assessed by reporting of AEs, ECG, vital sign measurements, clinical laboratory results, BCVA, slit lamp biomicroscopy, macroscopic hyperemia, pupil size, visual fields, dilated fundus examination, and subject comfort.

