## 6.2 Descriptive Statistics

Descriptive statistics will be provided in 3 areas: (1) demographics and baseline characteristics for Parts 1 and 2, (2) IOP analyses as noted in Sections 5.1 and 5.2 for Part 2, and (3) adverse events analysis for Part 2.

For continuous variables, descriptive statistics will include the number of subjects (n), mean, standard deviation (SD), median, minimum and maximum. Categorical variables will be summarized using absolute and relative frequencies (i.e., counts and percentages). All data to be summarized will be presented by cohort treatment groups using appropriate descriptive statistics.

Unscheduled data, such as information from unscheduled visits or investigator comments, will be included in the data listings. In general, these data will be excluded from the summary tables unless otherwise specified.

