## **10 SAFETY ANALYSIS**

Listings will be presented for all of the safety parameters (section 5.4) for Part 1 and 2 of the study, with the exception of adverse events, which will be summarized as described below. For slit-lamp biomicroscope and visual acuity parameters, potentially clinically significant findings will be flagged according to pre-defined criteria in the listings.

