#### **10.1.6 Other Safety Analysis**

A number of safety measures, for example: Clinical Laboratory Test, Urine Pregnancy Test, Physical Examination, Visual Fields, Macroscopic Hyperemia, Dilated Fundus Examination, Pupil Size, and Subject Comfort will only be presented in the listing.

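### Part 2 laboratory results are given in listings only, with no flag, no stated change from baseline and no by-arm summary, and the SAP does not declare this as a change from the protocol

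*Protocol*

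**What the plan says.** **Protocol.** Section 9.3 gives the general rule: "In general, data will be summarized with descriptive statistics which will include sample size, mean, standard deviation, median, minimum and maximum". Section 9.3.2 passes the detail on: "Detailed methods for analyses of all safety variables will be provided in the SAP". Section 7.5 has the laboratory data transferred to the sponsor or its designee at the end of each part, and gives statistical analysis as the reason. Section 12.2.1.7 requires the investigator to review each laboratory report and "record any clinically relevant changes occurring during the study in the AE section of the eCRF".

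Blood and urine are scheduled at Screening (Table 1, Section 8.2) and, in Part 2, at Day 14/Exit after the final dose (Table 3, Section 8.4.2). Nothing is scheduled at Baseline (Day -1). Part 1 has no post-dose laboratory sample (Table 2).

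**SAP.** Section 5.4 counts laboratory results among the safety endpoints: "Safety and tolerability will be assessed by reporting of AEs, ECG, vital sign measurements, clinical laboratory results, BCVA". Section 6.2 states "Descriptive statistics will be provided in 3 areas", and these are demographics and baseline characteristics, Part 2 IOP and Part 2 adverse events. Section 10 puts every safety parameter except adverse events in listings, and adds a flag for two of them: "For slit-lamp biomicroscope and visual acuity parameters, potentially clinically significant findings will be flagged". Section 10.1.6 names the clinical laboratory tests among the measures that "will only be presented in the listing". Section 1.1, which records changes from the protocol, covers the per-protocol analysis, the two-way ANOVA and the stratum subgroup. It does not cover laboratory data.

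**The concern.** A listing shows one subject at a time. It suits a single grossly abnormal value but not a modest move in the same direction across an arm. The only route from a laboratory value to a by-arm table is the investigator's judgement, subject by subject, that a change is clinically relevant and belongs in the adverse event section. A shift that stays within or near the reference range in most subjects would not pass that judgement, so no table would show it.

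This is the first study of the compound in humans (Protocol 1.4), and its purpose includes initial systemic safety (Protocol 2). Part 1 has no scheduled post-dose laboratory sample, so Day 14/Exit in Part 2 is the only scheduled on-treatment laboratory information in the trial. As planned, the report would contain no by-arm description of it to set beside timolol or to use in planning the next study.

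**Working it through.** No figure in the plan is at issue, so the main check is a comparison of text. The arithmetic only sizes the gap and the precision of the remedy.

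**Step 1. What each listed safety measure receives in the SAP (Part 2).**

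| Measure | Listing | Flag | Change from baseline stated | By-arm summary |
|---|---|---|---|---|
| Adverse events (10.1.1) | yes | not applicable | not applicable | yes |
| Slit-lamp findings (10.1.3) | yes | yes | used for the flag | no |
| Visual acuity (10.1.5) | yes | yes | used for the flag | no |
| ECG (10.1.2) | yes | no | yes | no |
| Vital signs (10.1.4) | yes | no | yes | no |
| Laboratory tests (10.1.6) | yes | no | no | no |

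SAP 6 has a general convention for calculating a change when there is no hour-matched value. It calls for no laboratory output and does not say which visit is the laboratory baseline. The one explicit definition, Day -1, stands in the IOP section (SAP 9.1), and no laboratory sample is scheduled on that day.

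**Step 2. Size of the listing.** Counting from Protocol 12.2.1.7, with neutrophil bands and segments and the three bilirubin fractions counted separately and red cell morphology left out, there are 15 numeric hematology and 29 numeric chemistry analytes: 15 + 29 = 44, or about 45. With 60 Part 2 subjects and two samples, 44 × 2 × 60 = 5,280 values, unflagged.

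**Step 3. Precision of a by-arm change.** The documents give no laboratory SD, so results are in units of the SD of the change, assumed equal across arms for the difference. Group sizes are 24 and 12 (Protocol 3).

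- One AGN-227535 arm: t(0.975, 23)/√24 = 2.069/4.899 = 0.42 SD.
- Timolol arm: t(0.975, 11)/√12 = 2.201/3.464 = 0.64 SD.
- Difference: t(0.975, 34) × √(1/24 + 1/12) = 2.032 × 0.3536 = 0.72 SD.

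**Step 4. How a shift would look in a listing (illustration, on assumptions).** Take a shift of 0.6 SD of the change, a normal distribution and a reference range covering the central 95%. Let r be the ratio of the SD of change to the between-subject SD; the documents do not give it. The expected number of 24 subjects above the upper limit is 24 × [1 − Φ(1.96 − 0.6r)]:

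- no shift: 24 × 0.025 = 0.6
- r = 0.5: 24 × 0.048 = 1.2
- r = 0.75: 24 × 0.066 = 1.6
- r = 1: 24 × 0.087 = 2.1

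So about 1 to 2 subjects would be above range against 0.6 expected, which a line-by-line listing would hardly reveal. The same 0.6 SD exceeds the one-arm half-width (0.42) but not the half-width against timolol (0.72).

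**Step 5. Chance findings.** If 95% intervals were read for 44 analytes in one arm with no true change, 44 × 0.05 = 2.2 would be expected to exclude zero. This is a reason to keep the tables descriptive.

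**The case against.** Four points on the other side carry weight.

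*No laboratory table was promised.* A reader might infer that the SAP breaks a specific commitment. The documents do not support that. The rule in Protocol 9.3 opens with a qualifier ("In general, data will be summarized with descriptive statistics"), and 9.3.2 leaves the methods to the SAP, which chose listings. Where 9.3.2 is specific, it concerns adverse events and peak hyperemia. What stands is an undeclared departure from a general rule, in a protocol that foresaw statistical analysis of these data (7.5).

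*Nothing is lost.* A reader might infer that a laboratory effect would go unreported. That is too strong. Every value is listed, each report is reviewed, and changes judged clinically relevant become adverse events, which SAP 10.1.1 tabulates by arm. The sponsor holds the data and could produce a table later. The accurate statement is that there is no planned group summary.

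*A by-arm table is weaker than it looks.* A one-sample t-test on 24 subjects would have about 80% power for a 0.6 SD shift, and it is tempting to cite this. But no test is proposed here, and the comparison that matters, against timolol, has about 38% power for the same shift. The power argument should not be used.

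*A one-arm change is confounded.* Screening blood is drawn before washout begins (Protocol 8.2). Washout can remove systemic carbonic anhydrase inhibitors, beta-blockers and other agents over up to 50 days. Samples are non-fasting and there is no placebo arm. A change within one arm therefore mixes drug effect with withdrawal of prior therapy and with time. This stands in full, and the table should say so.

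**Conclusion.** The gap is real and modest. Among the measures compared above, laboratory results receive the least: a listing, with no flag, no stated change and no by-arm summary. SAP 1.1 neither declares nor explains this. The consequence is limited to group shifts too small or too near normal for an investigator to call clinically relevant; larger individual changes have a route into the adverse event tables. The primary IOP analysis is unaffected.

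The textual finding needs no assumptions. The sizing rests on 24 and 12 subjects with paired samples, a common SD of change, and, for the illustration in Step 4, normality, a central-95% reference range and an unknown SD ratio taken from 0.5 to 1. A by-arm summary would describe the data. It would not settle whether a change is due to the drug. The trial's exploratory status argues against formal testing of laboratory values, but not against describing them.

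**What to change.** For Part 2 only, descriptive and without p-values, amend SAP 6.2 and 10.1.6 as follows:

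1. Summarise numeric hematology and chemistry analytes by arm (n, mean, SD, median, minimum and maximum) at Screening, at Day 14/Exit and for the change.
2. Add a by-arm shift table (low, normal, high before dosing against Day 14/Exit) using the central laboratory's reference ranges.
3. Flag out-of-range values in the listing.
4. Name the laboratory baseline as the last value before first dose. This is normally the Screening value, since no Day -1 sample is scheduled, and it also covers the single repeat test that the protocol allows.
5. State that Screening samples precede washout, so changes are to be read beside the timolol arm, with a 95% half-width for the difference of about 0.72 SD at 24 versus 12.

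If the sponsor prefers listings only, SAP 1.1 should at least record that choice and give the reason.

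The cost is SAP wording and programming of two standard tables from data already due to be transferred to the sponsor, with no new sample or visit. The downside is more output pages and some apparent shifts by chance across about 45 analytes.

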#### **9.4. Other Analyses**

#### **9.5. Subgroup Analyses**

For Part 2, descriptive statistics for the primary analyses will be provided by Baseline IOP stratum. Additional subgroup analyses may be specified in the SAP.

#### **9.6. Interim Analyses**

No interim statistical analysis is planned.

### **10. Supporting Documentation and Operational Considerations**

#### **10.1. Regulatory, Ethical, and Study Oversight Considerations**

##### **10.1.1. Regulatory and Ethical Considerations**

This study will be conducted in accordance with the protocol and with the following:

- Consensus ethical principles derived from international guidelines including the Declaration of Helsinki and Council for International Organizations of Medical Sciences (CIOMS) International Ethical Guidelines;
- Applicable ICH Good Clinical Practice (GCP) Guidelines;
- Applicable laws and regulations;
- The protocol, protocol amendments, ICF, Investigator Brochure, and other relevant documents (eg, advertisements) must be submitted to an IRB/IEC by the investigator and reviewed and approved by the IRB/IEC before the study is initiated;

- Any amendments to the protocol will require IRB/IEC approval before implementation of changes made to the study design, except for changes necessary to eliminate an immediate hazard to study subjects;
- The investigator will be responsible for the following:
  - Providing written summaries of the status of the study to the IRB/IEC annually or more frequently in accordance with the requirements, policies, and procedures established by the IRB/IEC
  - Notifying the IRB/IEC of SAEs or other significant safety findings as required by IRB/IEC procedures
  - Providing oversight of the conduct of the study at the site and adherence to requirements of US 21 CFR, ICH guidelines, the IRB/IEC, and all other applicable local regulations.

#### **10.1.2. Financial Disclosure**

Investigators and sub-investigators will provide the sponsor with sufficient, accurate financial information as requested to allow the sponsor to submit complete and accurate financial certification or disclosure statements to the appropriate regulatory authorities. Investigators are responsible for providing information on financial interests during the course of the study and for 1 year after completion of the study.

#### **10.1.3. Informed Consent Process**

- The investigator or his/her representative will explain the nature of the study to the participant or his/her legally authorized representative and answer all questions regarding the study;
- Subjects must be informed that their participation is voluntary. Subjects or their legally authorized representative will be required to sign a statement of informed consent that meets the requirements of US 21 CFR 50, local regulations, ICH guidelines, Health Insurance Portability and Accountability Act (HIPAA) requirements, where applicable, and the IRB/IEC or study center;
- The medical record/source document must include a statement that written informed consent was obtained before the subject was entered in the study and the date the written consent was obtained. The authorized person obtaining the informed consent must also sign the ICF;
- If the ICF is modified during the subject's participation in the study, it may be required for the subject to be re-consented;
- A copy of the ICF(s) must be provided to the subject or the subject's legally authorized representative.

#### **10.1.4. Data Protection**

- Subjects will be assigned a unique identifier by the sponsor. Any participant records or datasets that are transferred to the sponsor will contain the identifier only; participant names or any information which would make the participant identifiable will not be transferred;
- The subject must be informed that his/her personal study-related data will be used by the sponsor in accordance with local data protection law. The level of disclosure must also be explained to the subject;
- The subject must be informed that his/her medical records may be examined by Clinical Quality Assurance auditors or other authorized personnel appointed by the sponsor, by appropriate IRB/IEC members, and by inspectors from regulatory authorities.

#### **10.1.5. Coordinating Investigator**

A signatory Coordinating Investigator will be designated prior to the writing of the Clinical Study Report.

### **10.2. Protection of Human Subjects**

#### **10.2.1. Subject Confidentiality**

A report of the results of this study may be published or sent to the appropriate health authorities in any country in which the study drug may ultimately be marketed, but the subject's name will not be disclosed in these documents. The subject's name may be disclosed to Whitecap Biosciences or the governing health authorities (eg, US FDA, Canadian Committee for Medicinal Products for Human Use [CHMP], US Pharmaceutical and Medical Devices Agency, Japan PMDA) if they inspect the study records. Appropriate precautions will be taken to maintain confidentiality of medical records and personal information.

#### **10.2.2. Subject Privacy**

Written authorization and other documentation in accordance with the country and local privacy requirements (where applicable) is to be obtained from each subject prior to enrollment into the study, and/or from the subject's legally authorized representative in accordance with the applicable privacy requirements (eg, the Health Insurance Portability and Accountability Act Standards for Privacy of Individually Identifiable Health Information ("HIPAA").

In accordance with country-specific requirements, additional purposes of this study may include publishing of anonymized subject data from the study.

